10.1 Subject Disposition

Study completion and discontinuation details, eligibility, treatment allocation, population assignment, and protocol deviations will be listed.

The number of subjects screened, randomized, receiving and completing double-blind treatment and the primary reasons for any study treatment discontinuations in the double-blind phase will be tabulated. A subject is considered to have completed the double-blind phase if they have attended Visit 4 without having discontinued the study.

The number of subjects starting and completing each of the open-label phases and the primary reasons for discontinuation in each of the open-label phases will be tabulated. A subject is considered to have started the first (second) open-label phase if they have been supplied with study treatment at Visit 4 (Visit 5). They are considered to have completed the first (second) open-label phase if they have attended Visit 5 (Visit 8) without having discontinued the study.

The number and percentage of subjects in each analysis population will be tabulated. The number and percentage of subjects in each center and in each geographic region (US and Europe) will be tabulated.

10.2 Demographic and Baseline Characteristics

Demographic parameters will include date of birth, age, sex, race, ethnicity and screening body weight, height and BMI.

Age will be derived from the birth date and screening date as using the following SAS code:

```
Age=floor ((intck('month',birth,screen) - (day(screen) < day(birth))) / 12)
```

Body weight and height will be measured at Screening. Body mass index (BMI) at screening will be programmatically calculated in the eCRF.

Demographics will be listed and tabulated using descriptive statistics.

The following baseline characteristics will also be tabulated:

- ADHD (Yes, No; identified from the medical history)
- Epilepsy (Yes, No)
- Prior Anti-Epileptic Treatment (ATC code N03)
- Prior Anti-Depressant Treatment (selective serotonin reuptake inhibitor [SSRIs] ATC code N06AB)
- Prior Beta-Blockers Use (ATC code C07)
- Prior Stimulant Use (ATC code N06B)
- Prior ADHD Treatment (Ritalin ATC code N06BA04)
- Prior Clonidine Use (ATC code C02AC01)

10.3 Neurodevelopmental Disability

Details of the diagnosis of neurodevelopmental disability will be listed and tabulated. The time since first diagnosis of neurodevelopmental disability (in months) will be calculated from date of informed consent and summarized descriptively.

10.4 Melatonin Use

Details of melatonin use will be listed and tabulated.

10.5 Medical History

Details of medical history will be listed including condition, start and stop dates. Partial dates may be recorded in the electronic data capture system and no imputations will be made for missing or partial dates in the listing.

Medical histories will be coded according to the Medical Dictionary for Regulatory Activities (MedDRA) version 18 or higher. A summary of medical histories and number of subjects with a medical history will be presented by System Organ Class and Preferred Term.

10.6 Prior and Concomitant Medications

Concomitant medications recorded during the study will be coded using World Health Organization (WHO)-Drug. Details of concomitant medication will be listed.

Concomitant medications will be summarized according to whether they were being taken pre-study (prior medications) and/or during the study (concomitant medication). Prior medications are any that were being taken prior to the first dose of study medication (medication stop date prior to the first dose of study medication). Concomitant medications are any that were being taken on or after the first dose of study medication. If the start and stop dates of the concomitant medications do not clearly define the period during which a medication was taken, it will be assumed to be a concomitant medication.

Concomitant medications will be assigned to the phase they were taken: Double-Blind, first Open-Label, second Open-Label. If a concomitant medication starts or is ongoing between Visit 2 and Visit 4, it will be assigned to the Double-Blind phase. If a concomitant medication starts or is ongoing between Visit 4 + 1 day and Visit 5, it will be assigned to the first Open-Label phase. If a concomitant medication starts or is ongoing between Visit 5 + 1 day and Visit 8, it will be assigned to the second Open-Label phase. If the start and stop dates of the concomitant medications do not clearly define the phase during which a medication was taken, it will be assumed to be taken across all phases.

Prior and concomitant medications will be summarized by Anatomical Therapeutic Chemical (ATC) level 2 term and preferred term.

Details of non-pharmacological concomitant measures will be listed.

11 Efficacy

Subjects will be classified and summarized by randomized treatment. For all efficacy assessments, the baseline values will be calculated as the last recorded value prior to the start of randomized treatment. Change from baseline values will be calculated as the assessment score minus the baseline value. For questionnaires the change from baseline values will be calculated for each item and total/subscale score as applicable.

All summaries and analyses will be performed on the FAS set. The primary efficacy endpoint and select secondary efficacy endpoints will also be analyzed on the PP set. Analyses looking at the impact missing data on the primary efficacy endpoint will also be performed on the All Randomized set.

11.1 Primary Efficacy Variable

11.1.1 Total Sleep Time (TST)

TST will be assessed by a Sleep and Nap Diary.

Daily TST will be calculated programmatically as follows:

the time the child woke up in the morning *minus*

the time the child went to bed *minus*

the time taken to fall asleep *minus*

the total duration of any night awakenings

If the time the child went to bed and the time they woke up in the morning are the same, the TST will be set to 0.

The number of daily diaries with data recorded and the number of daily diaries with a valid mean TST will be tabulated by scheduled visit.

For each subject the mean TST will then be calculated as the mean of the last 14 days prior to each scheduled visit. A subject will be required to have a minimum of 3 nightly TST values per week (6 nights in total) in order to have a valid mean TST after baseline. A subject will be required to have a minimum of 6

nightly TST values across the 2 weeks in order to have a valid mean TST at baseline. The mean TST and change from baseline in mean TST will be summarized by scheduled visit using descriptive statistics. The change from baseline in mean TST will be plotted over time. Empirical cumulative distribution functions by treatment group will be plotted for change from baseline in mean TST at Visit 4 (Week 15).

The change from baseline in mean TST will be analyzed using a mixed-effects model for repeated-measures (MMRM). The model will contain the TST at Visit 3 (Week 5) and Visit 4 (Week 15) as the dependent variable, with fixed effects for visit, the mean baseline TST, randomized treatment and the mean baseline TST and randomised treatment both nested within visit. Visit-to-visit repeated measures will assume a general (unstructured) covariance structure. Standard errors and degrees of freedom for significance tests will be derived using the Kenward-Roger method [1].

From this model, the adjusted mean change from baseline (and standard error) in TST after 13 weeks of treatment for each treatment group will be calculated and the associated 95% confidence intervals (CI) for the change presented. Furthermore, the estimated difference (and standard error) between treatments will be estimated, the associated 95% CI presented and the null hypothesis that these means are equal will be tested.

Example SAS code for this analysis is given below:

```
proc mixed data=tst method=reml;
  class subjid trtp avisitn;
  model chg=trtp avisitn base trtp(avisitn) base(avisitn)/ddfm=kr;
  repeated avisitn/subject=subjid type=un;
  lsmeans trtp(avisitn)/diff cl om;
  ods output lsmeans=lsm(where=(avisitn=4)) diffs=diff(where=(avisitn=4));
run;
```

In addition, the effect size will be calculated based on Cohen's d (mean difference between groups/pooled standard deviation) where the mean difference is adjusted for other model factors using MMRM and the pooled standard deviation is evaluated using the model standard errors as follows:

$$sd_{pool} = \sqrt{\left((se_{circ} * se_{circ} * (n_{circ} - 1) * n_{circ}) + (se_{plac} * se_{plac} * (n_{plac} - 1) * n_{plac}) \right) / (n_{circ} + n_{plac} - 2)}$$

where n_{circ} and n_{plac} are the number of subjects with a measurement at Visit 4 (Week 15) and se_{circ} and se_{plac} are the standard errors of the adjusted means in the Circadin and Placebo groups respectively.

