6.1 Sample Size

To achieve 95% power at the 5% level for the primary objective (assuming a change of 0.72 hour in the Circadin® arm and 0.27 hour in the placebo arm and a standard deviation (SD) of 0.69 in the Circadin® arm and 0.45 in the placebo arm), 45 subjects are required per combined group. Therefore, 90 subjects in total are required to complete Visit 5. These estimations are based on previous studies conducted with Circadin®.

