6.2 Randomization

At Visit 1, enough eligible male and female children, of ages 2 to 17.5 years, will be screened for the study to allow for 120 subjects to then be randomized in a 1:1 ratio to receive Circadin® or placebo at Visit 2. A minimum of 90 children are expected to complete the double-blind and first open-label period (up to Week 28). A minimum of 50 children are expected to complete the second open-label safety follow-up period.

7 Protocol Deviations

Major protocol deviations are defined as those deviations from the study protocol that may have the ability to impact the efficacy results. As such, subjects with major deviations occurring up to the end of the double-blind phase will be excluded from the per-protocol (PP) population (as defined in Section 8.5).

Major protocol deviations include (but are not limited to):

- Deviation from inclusion/exclusion criteria
- Withdrawal criteria met during the study but subject was not withdrawn
- Prohibited concomitant medications
- Substantial deviations from the dosing schedule (Subjects received at least 5 of 7 doses in the week prior to the scheduled visit and treatment compliance is within the range >60%)
- Substantial deviations in the completion of the sleep and nap diary (Subjects must have completed the diary at least 3 out of 7 nights per week over the two weeks prior to the scheduled visit and have a valid mean TST value at Visit 4)

Where possible, major deviations will be programmatically verified by Datatrial. Listings of concomitant medications in Excel format will be provided to the sponsor by Datatrial for review to identify prohibited medications prior to unblinding.

Major protocol deviations occurring up to the end of the first open-label phase will be identified during a Blinded Data Review Meeting (BDRM) prior to database lock and unblinding.

The purpose of the BDRM will be two-fold; It will be used to review and confirm the data identified as protocol deviations as detailed above. It will also be used to review the Sleep and Nap diary and confirm that the data is correct and/or identify implausible values and document any changes that are made to the source data. Blinded SAS listings of the Sleep and Nap diary data including derivation of mean TST will be provided by

Datatrial in advance of the BDRM to aid this review. Any changes to the source data may require a further review of the protocol deviations.

8 Analysis Populations

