11.6 Subgroup Analysis

11.6.1 Inclusion of Additional Factors in MMRM Analysis

The effect of treatment in subgroups of interest will be assessed by repeating the analysis of the primary efficacy variable by including the following factors in the model, one at a time.

- Geographic region (US v Europe)
- Center
- Age (2-<6 yrs, 6-<12 yrs, >-12 yrs)
- Gender
- ADHD (Yes, No; identified from the medical history)
- Austim Type
- Epilepsy (Yes, No)
- Prior Anti-Epileptic Treatment
- Prior Anti-Depressant Treatment
- Prior Beta-Blockers Use
- Prior Stimulant Use
- Prior ADHD Treatment
- Prior Clonidine Use

From this model, within each subgroup, the adjusted mean change from baseline (and standard error) in TST after 13 weeks of treatment for each treatment group will be calculated and the associated 95% CI for the change presented. Furthermore for each subgroup, the estimated difference (and standard error) between treatments will be estimated, the associated 95% CI presented and the null hypothesis that these means are equal will be tested.

Example SAS code for this analysis is given below:

```
proc mixed data=tst method=reml;  
  class subjid trtp avisitn geog;  
  model chg=trtp avisitn base geog trtp*geog trtp(avisitn) base(avisitn)  
geog(avisitn) trtp*geog(avisitn)/ddfm=kr;  
  repeated avisitn/subject=subjid type=un;
```

```
lsmeans trtp*geog(avisitn)/diff cl om;  
ods output lsmeans=lsmeans(where=(avisitn=4)) diff=diff(where=(avisitn=4 and  
geog=_geog));  
run;
```

The above analysis will be repeated for CSDI, CGAS and Total SDQ at 13 weeks incorporating the following factors into the model:

- ADHD (Yes, No)
- Epilepsy (Yes, No)
- Prior ADHD Treatment
- Prior Clonidine Use

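### The primary MMRM adjusts for baseline TST but not for age in children aged 2 to 17.5 years; prespecifying age is a cheap refinement, probably of modest benefit, and its absence is not a validity error

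*SAP*

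**What the plan says.** SAP 11.1.1 models change from baseline in mean TST at Weeks 5 and 15 "with fixed effects for visit, the mean baseline TST, randomized treatment and the mean baseline TST and randomised treatment both nested within visit". The example code agrees, and its nested baseline term gives a separate baseline slope at each visit. Protocol 12.8.1 lists the same covariates for its base MMRM: baseline score, visit and treatment. Neither has an age term.

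The age range is wide: SAP 6.2 says "enough eligible male and female children, of ages 2 to 17.5 years, will be screened". Age is derived from birth date and screening date in whole years (SAP 10.2), and age in months is already needed for the BMI Z-scores (SAP 12.5).

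Age enters an efficacy model only in SAP 11.6.1, as "Age (2-<6 yrs, 6-<12 yrs, >-12 yrs" in a list of 13 factors added one at a time. The example code there includes the treatment-by-factor interaction, and the output is a treatment difference within each subgroup.

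Neither SAP 6.2 nor protocol 12.4 mentions stratification. Protocol 12.4 refers the randomization procedure to guidelines that are not among these documents.

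**The concern.** Sleep duration may well depend on age over a range of 15.5 years, and the protocol ties dosing to an age-appropriate bedtime. Baseline TST carries part of that dependence, but not necessarily all of it. A child's baseline reflects the norm for the child's age plus a deviation from that norm, made up of severity and night-to-night noise. If the norm persists to Week 15 while the deviation partly regresses, a single slope on baseline at that visit cannot fit both parts, and age still predicts the outcome.

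Some regression is plausible. Children must still meet the sleep-problem criteria on the run-in diary that also supplies baseline TST, and a valid baseline mean may rest on as few as 6 nights.

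At stake are some avoidable width in the interval for the primary effect and a chance age difference between arms that is only partly corrected.

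**Working it through.** **1. The plan's own figure.** Inputs from SAP 6.1: "assuming a change of 0.72 hour in the Circadin® arm and 0.27 hour in the placebo arm", so the difference is 0.72 - 0.27 = 0.45 h; "standard deviation (SD) of 0.69 in the Circadin® arm and 0.45 in the placebo arm"; 5% level (two-sided assumed, as sidedness is not stated).

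- SD = sqrt((0.69² + 0.45²)/2) = sqrt(0.3393) = 0.582 h.
- SE at 45 per arm = 0.582 × sqrt(2/45) = 0.123 h.
- Noncentral t power is 95.2% at 45 per arm (95.1% by Welch) and 94.8% at 44.

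The stated "45 subjects are required per combined group" reproduces. It does not depend on age.

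**2. What an age term does, for any strength of association.** Let r be the partial correlation of age with Week 15 TST change given baseline TST. With N = 90, the SE is multiplied by sqrt(1 - r²) × sqrt((N-4)/(N-5)). The second factor is sqrt(86/85) = 1.006, the cost when age adds nothing. Break-even is |r| = sqrt(1/86) = 0.11.

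| r (assumed) | Residual variance cut | Power at 0.45 h | Power at 0.30 h |
|---|---|---|---|
| no age term | - | 95.2% | 67.6% |
| 0 | 0% | 95.0% | 67.1% |
| 0.1 | 1% | 95.2% | 67.5% |
| 0.2 | 4% | 95.7% | 68.8% |
| 0.3 | 9% | 96.5% | 71.1% |
| 0.5 | 25% | 98.6% | 79.2% |

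The documents give no r. The 0.30 h effect is an assumption; the plan assumes 0.45 h.

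**3. What r might be.** Assumed, not in the documents: TST falls by g = 0.1-0.3 h per year of age; within-age SD s = 1.0-1.25 h; a fraction λ of the within-age deviation persists to Week 15; residual SD 0.5 h; ages uniform over 2-17.5 years, so SD 15.5/sqrt(12) = 4.47 years and variance 20.02. The age norm itself is taken to persist fully.

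Baseline = -g·age + w and Week 15 = -g·age + λw + e. Substituting for w, the age coefficient given baseline is -(1-λ)g, which is zero only if λ = 1 or g = 0. With A = 20.02g², residual variance without age is 0.25 + (1-λ)²·A·s²/(A + s²), and with age it is 0.25.

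- λ = 0.75, g = 0.1, s = 1: extra 0.0625 × 0.2002/1.2002 = 0.0104; cut 0.0104/0.2604 = 4%.
- λ = 0.75, g = 0.3, s = 1.25: extra 0.0625 × 1.802 × 1.5625/3.364 = 0.0523; cut 0.0523/0.3023 = 17%.

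| λ | Variance cut | Implied r | Implied SD of change |
|---|---|---|---|
| 0.90 | 1-3% | 0.08-0.18 | 0.51-0.52 h |
| 0.75 | 4-17% | 0.20-0.42 | 0.56-0.59 h |
| 0.60 | 10-35% | 0.31-0.59 | 0.64-0.71 h |

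The SD of change is sqrt((1-λ)²s² + 0.25). The 75% row brackets the plan's 0.582 h. The 35% corner implies 0.71 h, above both planned SDs, so I do not rely on it.

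Power at 45 per arm and λ = 0.75, using these residual SDs:

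- 0.45 h: from 97.0-98.5% to 98.8% (98.7% after the 1.006 factor).
- 0.30 h: from 73-79% to 80%.

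These start above 95.2% because step 1 uses the SD of raw change, without baseline adjustment.

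**4. Chance imbalance.** With 60 per arm ("120 subjects to then be randomized in a 1:1 ratio") and uniform ages, the SE of the difference in mean age is 4.47 × sqrt(2/60) = 0.82 years, so 1.96 SE is 1.6 years. If the within-age deviation is balanced, the baseline-only estimate shifts by g(1-λ)s²/(A + s²) per year of imbalance. For 1.6 years that is 2.0-3.3 minutes at λ = 0.75 and 0.8-1.3 minutes at λ = 0.90, against a planned effect of 27 minutes.

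**The case against.** The strongest reply is that this is a preference, not an error. Randomization keeps the test valid without age, the covariates match the protocol, and the planned power is reached without an age term. All of that stands. A reader might infer that leaving age out biases the primary result or undermines the test; nothing in the documents supports that.

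The second reply is that the benefit is assumed. That also stands. Slope, persistence and within-age SD are not in the documents, and the calculation lets the age part persist in full while only the remainder regresses. The entry cut-offs are the same at every age, so the age gradient among those selected may be weaker than assumed. The residual SD of 0.5 h is itself above the planned placebo SD of 0.45 h. It would therefore be too strong to say that age will certainly remove variance, or will do so at no cost: below |r| of about 0.11 the SE rises slightly, and at 90% persistence with a shallow age slope r is only 0.08.

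A reader might also infer that randomization is unstratified by age. The documents describe no stratification, but the procedure is held elsewhere, so this cannot be settled here.

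Finally, SAP 11.6.1 already uses age. That does not answer the point, because its model reports effects within age bands and gives no overall age-adjusted estimate.

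**Conclusion.** The point holds as an optional improvement. The primary model omits a baseline variable that the trial already holds, in a population where it plausibly matters, and no other planned analysis supplies the overall age-adjusted effect.

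The gain is probable but unproven and, at the planned effect, small: at most about 2 points of power at 75% persistence and almost none at 90%. It would matter more if the true effect were smaller than 0.45 h. These sizes rest wholly on the assumed slope, spread, persistence and uniform age distribution. The downside is small and known.

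**What to change.** Record the change in SAP Section 14 before database lock and unblinding; added after unblinding it would be post hoc.

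- In SAP 11.1.1, add continuous age, derived from birth date, and age nested within visit to the primary TST MMRM (text and code). The whole-year age in SAP 10.2 is coarser, so state the new derivation.
- In SAP 11.5, add age to the ANCOVA used for the MI and BOCF analyses of TST.
- State the scope. Many endpoints are analysed by reference to the TST method and would inherit the term silently. Say whether it applies to the other child sleep endpoints, and that it does not carry over to the caregiver scales (ESS, PSQI, WHO-5) or the age-standardised BMI Z-score.
- In the SAP 11.6.1 age-subgroup model, use the age categories in place of continuous age, so that age is not entered twice.

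The cost is a few lines of SAP text and code, one degree of freedom per visit, and an SE increase of at most about 0.6% if age adds nothing. No new data are needed. If the sponsor prefers to keep the protocol's covariates for the primary model, a prespecified age-adjusted sensitivity analysis is the minimum.

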16.1 List of Tables

Table Number	Table Title	Population
Table 14.1.1.1	Patient Disposition: Double Blind Phase	All Enrolled Set
Table 14.1.1.2	Patient Disposition: First Open Label Phase	All Enrolled Set
Table 14.1.1.3	Patient Disposition: Second Open Label Phase	All Enrolled Set
Table 14.1.2.1	Demographic Characteristics	All Enrolled Set
Table 14.1.2.2	Demographic Characteristics	All Randomized Set
Table 14.1.3	Baseline Characteristics	All Randomized Set
Table 14.1.4	Diagnosis of Neurodevelopmental Disability	All Randomized Set
Table 14.1.5	Melatonin Use	All Randomized Set
Table 14.1.6	Medical History	All Randomized Set
Table 14.1.7	Prior Medications	All Randomized Set
Table 14.1.8	Concomitant Medications - Double Blind Phase	All Randomized Set
Table 14.1.9	Concomitant Medications - First Open Label Phase	All Randomized Set
Table 14.1.10	Concomitant Medications - Second Open Label Phase	All Randomized Set
Table 14.2.1.1	Number of Sleep and Nap Diaries with Data Recorded	FAS Set
Table 14.2.1.2	Number of Sleep and Nap Diaries with a Valid TST	FAS Set
Table 14.2.1.3	SND Total Sleep Time and Change from Baseline – Double Blind - Descriptive Statistics	FAS Set
Table 14.2.1.4	SND Total Sleep Time Change from Baseline at 13 Weeks Double Blind – MMRM Analysis	FAS Set
Table 14.2.1.5	SND Total Sleep Time Change from Baseline at 13 Weeks Double Blind – MMRM Analysis	Per Protocol Set
Table 14.2.1.6	SND Sleep Latency and Change from Baseline – Double Blind - Descriptive Statistics	FAS Set
Table 14.2.1.7	SND Sleep Latency Change from Baseline at 13 Weeks Double Blind – MMRM Analysis	FAS Set
Table 14.2.1.8	SND Sleep Latency Change from Baseline at 13 Weeks Double Blind – MMRM Analysis	Per Protocol Set

Table Number	Table Title	Population
Table 14.2.1.9	SND Duration of Wake and Change from Baseline – Double Blind - Descriptive Statistics	FAS Set
Table 14.2.1.10	SND Duration of Wake Change from Baseline at 13 Weeks Double Blind – MMRM Analysis	FAS Set
Table 14.2.1.11	SND Duration of Wake Change from Baseline at 13 Weeks Double Blind – MMRM Analysis	Per Protocol Set
Table 14.2.1.12	SND Number of Awakenings and Change from Baseline – Double Blind - Descriptive Statistics	FAS Set
Table 14.2.1.13	SND Number of Awakenings Change from Baseline at 13 Weeks Double Blind – MMRM Analysis	FAS Set
Table 14.2.1.14	SND Number of Awakenings Change from Baseline at 13 Weeks Double Blind – MMRM Analysis	Per Protocol Set

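### If the planning SDs of TST change (0.69 h and 0.45 h) recur as residual SDs, the shared-covariance MMRM gives arm-level 95% CIs that cover about 90% (Circadin) and 99% (placebo), and the primary test keeps its level only at similar completer numbers

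*SAP*

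**What the plan says.** SAP 6.1 (like Protocol 12.6) bases the sample size on TST, "assuming a change of 0.72 hour in the Circadin® arm and 0.27 hour in the placebo arm", with "a standard deviation (SD) of 0.69 in the Circadin® arm and 0.45 in the placebo arm". It attributes these figures to previous Circadin studies.

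For the analysis, SAP 11.1.1 states: "Visit-to-visit repeated measures will assume a general (unstructured) covariance structure". The example code has "repeated avisitn/subject=subjid type=un". With no GROUP= option, both arms share one 2×2 visit covariance matrix, and the text does not mention separate matrices by arm either. SEs and degrees of freedom use Kenward-Roger.

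The arm-level results come out of that fit: "the adjusted mean change from baseline (and standard error) in TST after 13 weeks of treatment for each treatment group will be calculated", with a 95% CI for each arm. The difference, its CI and its test follow. These results go to Table 14.2.1.4, "SND Total Sleep Time Change from Baseline at 13 Weeks Double Blind – MMRM Analysis". The arm SEs are also used for Cohen's d, where "the pooled standard deviation is evaluated using the model standard errors as follows".

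SDs by arm will appear in Table 14.2.1.3, "SND Total Sleep Time and Change from Baseline – Double Blind - Descriptive Statistics".

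**The concern.** The plan expects the Circadin arm to be about one and a half times as variable as the placebo arm, yet its primary model assumes equal variances. A shared variance gives both arms the same SE at equal numbers, too small for the more variable arm and too large for the other. Kenward-Roger corrects for small samples under the assumed covariance; it does not repair a wrong equal-variance assumption.

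No other planned TST analysis relaxes the assumption. The per-protocol MMRM is the same model, and the multiple-imputation and BOCF analyses use an ANCOVA with one residual variance.

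Two things are at stake. The primary table goes into the report submitted for approval, with arm-level intervals labelled 95%. The level of the primary test also depends on how evenly children complete the double-blind phase.

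**Working it through.** **Inputs.** SAP 6.1: changes 0.72 h and 0.27 h, so a difference of 0.45 h; SDs 0.69 h (Circadin) and 0.45 h (placebo), ratio 1.53; 95% power at the 5% level; 45 per arm. SAP 6.2: 120 randomized 1:1, at least 90 completing to Week 28. Unequal completer splits below are assumed.

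**1. The plan's own figure.** n per arm = (1.96 + 1.645)² × (0.69² + 0.45²)/0.45² = 43.55, so 44 by the normal approximation. With the noncentral t, power is 94.8% at 44 and 95.2% at 45. The stated 45 per arm reproduces.

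**2. Arm-level SEs at 45/45.** Shared SD = √((0.69² + 0.45²)/2) = 0.5825 h.

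| | Shared SE | Arm-specific SE | Width ratio | Error in half-width |
|---|---|---|---|---|
| Circadin | 0.5825/√45 = 0.0868 h | 0.69/√45 = 0.1029 h | 0.844 | 1.96 × 0.0161 h = 1.9 min too narrow |
| Placebo | 0.0868 h | 0.45/√45 = 0.0671 h | 1.294 | 1.96 × 0.0197 h = 2.3 min too wide |

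**3. Arm-level coverage.** Coverage = 2Φ(1.96 × 0.5825/SD) − 1.
- Circadin: 2Φ(1.655) − 1 = 90.2%
- Placebo: 2Φ(2.537) − 1 = 98.9%

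MMRM simulation of the planned model at 45/45 gives 90.2% to 90.7% and 98.8% for visit correlations of 0.3 to 0.8. Setting the Week 5 SDs equal, or having nobody missing at 60/60, leaves this essentially unchanged.

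**4. Dependence on the residual SD ratio r.** Circadin coverage is 2Φ(1.96√((1 + 1/r²)/2)) − 1. Placebo coverage is 2Φ(1.96√((1 + r²)/2)) − 1.

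| r | Circadin | Placebo |
|---|---|---|
| 1.0 | 95% | 95% |
| 1.2 | 92.9% | 97.0% |
| 1.35 | 91.5% | 98.0% |
| 1.53 | 90.2% | 98.9% |
| 1.67 | 89.4% | 99.3% |
| 1.92 | 88.2% | 99.7% |

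The last two rows apply if baseline adjustment removes the same absolute variance (assumed 0.05 or 0.10 h²) from both arms.

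**5. The test of the difference.** The model's SE is s√(1/n₁ + 1/n₂), where s² = ((n₁−1)0.69² + (n₂−1)0.45²)/(n₁+n₂−2). The true SE is √(0.69²/n₁ + 0.45²/n₂). Type I error ≈ 2(1 − Φ(1.96 × ratio)), with Circadin completers listed first.

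| Completers | Model SE (h) | True SE (h) | Ratio | Type I error | Simulated ANCOVA |
|---|---|---|---|---|---|
| 45/45 | 0.1228 | 0.1228 | 1.000 | 5.0% | 5.1% |
| 40/50 | 0.1207 | 0.1263 | 0.956 | 6.1% | 6.2% |
| 35/55 | 0.1200 | 0.1315 | 0.913 | 7.35% | 7.3% |
| 50/40 | 0.1264 | 0.1208 | 1.046 | 4.0% | 4.2% |
| 55/35 | 0.1316 | 0.1202 | 1.095 | 3.2% | 3.3% |

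These are complete-case figures. Two MMRM simulations that also used Week 5 data disagree on how much it helps. One gave 5.5% at 40/50 (difference CI coverage 94.5%). The other, with 35% Circadin and 15% placebo dropout from 60 per arm (39/51 expected), gave 6.9%, using simplified degrees of freedom and 3,000 runs.

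**6. Arm-specific covariance.** With `group=trtp`, simulated MMRM arm coverage is 94.4% to 95.7% in every scenario. A complete-case analysis with arm-specific variances keeps coverage of the difference at 94.8% to 95.1% at 45/45, 40/50, 35/55 and 50/40.

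**The case against.** The case for leaving the SAP alone has weight.

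- **The premise is conditional.** SAP 6.1 gives SDs of change used for sizing, not baseline-adjusted residual SDs, and simulation adds no evidence that the ratio will recur. This stands. A reader might infer that the arm-level intervals are certain to be wrong; the documents do not support that, and at a ratio of 1.0 there is no error.
- **The size is modest.** About 2 minutes of half-width is small against a planned difference of 27 minutes and a TST responder threshold of 45 minutes (SAP 11.3.1). This stands.
- **The objective is comparative.** The Week 15 test concerns the difference, so the arm-level intervals are descriptive. This stands, but an interval labelled 95% should be near 95% under the assumptions that sized the trial.
- **Unequal spread will be visible** in Table 14.2.1.3 and in the planned cumulative distribution plots. This stands in part: those displays are unadjusted and do not correct the model-based intervals.
- **The code is labelled an example.** True, but the accompanying text specifies no arm-specific covariance either.

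Two stronger readings are tempting. A reader might infer that the primary test or the sample size is invalid. It is not: at 45/45 the two SEs of the difference are identical, and 45 per arm reproduces. A reader might instead infer that the primary test is safe whatever happens. That is not supported either, because its level depends on completer balance, and the SAP itself lists dropout by arm as a secondary endpoint to be compared (4.2, 11.2.5).

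**Conclusion.** The point holds as a conditional one and deserves a small SAP change. If the planning SD ratio of 1.53 persists in the residuals, the arm-level 95% CIs for TST in Table 14.2.1.4 cover about 90% for Circadin and 99% for placebo, with half-widths wrong by about 2 minutes in opposite directions. No document gives residual SDs by arm, so confidence is medium.

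The primary test keeps its 5% level at similar completer numbers. It becomes mildly liberal, about 6% to 7% in the complete-case calculation, if clearly fewer Circadin than placebo children complete, and conservative in the reverse case. How far the MMRM's Week 5 data reduce this is unsettled. The point is limited to TST, the only endpoint for which the plan documents unequal SDs. Cohen's d is hardly affected: 0.81 with either set of SEs at 45/45, and 0.83 against 0.84 at 40/50.

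**What to change.** 1. Keep the common-covariance MMRM as the primary analysis, with all of Table 14.2.1.4 and Cohen's d on that one model. Then the arm means and the difference in the table come from a single fit.
2. Pre-specify one sensitivity analysis of TST: the same model with `group=trtp` added to the REPEATED statement, with Kenward-Roger, falling back to the common-covariance model if it does not converge.
3. Report it in a separate table at Weeks 5 and 15: arm-level adjusted means, SEs and 95% CIs, and the difference with its CI and p-value.
4. Footnote Tables 14.2.1.4, 14.2.1.5 (per protocol) and 14.2.6.1 (3 weeks, which SAP 11.3.1 takes from the same model): their arm-level CIs assume equal variances; refer to the sensitivity table.

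Other endpoints and the subgroup models in SAP 11.6.1 stay as planned.

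**Cost.** SAP wording, one extra fit, one table and three footnotes; no change to sample size, primary test or power. Arm-level degrees of freedom in the sensitivity fit fall from about 100 to about 50. If the SDs prove equal, its arm CI half-width is 0.166 h instead of 0.164 h. There were no convergence failures in 80,000 simulated trials fitted both ways, so the fallback should rarely be needed.
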